Evidence shows that patients with STEMI and multivessel disease have a worse outcome in survival compared to those without multivessel disease and that there is a higher rate of post-MI heart failure in patients with multivessel disease, probably due to persistent myocardial ischemia.

Fractional flow reserve (FFR) has become the golden standard in cathlab method for defining flow-limiting coronary lesions requiring mechanical revascularisation in patients with stable angina pectoris. The FFR measurements in non culprit lesions compared to angiographic assessment only have recently been proven to be safe and accurate even in setting of STEMI.

Primary Percutaneous Coronary Intervention (PPCI) has been established as the preferred revascularisation technique for STEMI patients. The actual ESC and AHA/ACC guidelines do not recommend complete revascularisation during primary PCI. However, these recommendations are based on limited and outdated clinical evidence and whether these recommendations hold true in current interventional cardiology practice need to be investigated.

Therefore, a prospective randomised trial in patients with multivessel disease presenting with STEMI to evaluate a strategy of FFR-guided complete revascularisation during primary PCI compared to primary PCI of culprit vessel only followed by staged revascularisation of non-IRA in case of proven ischemia or persistence of symptoms of angina as indicated from the guidelines, in patients with multivessel disease presenting with STEMI, is needed.

Patients will be randomised after successful revascularisation of the culprit vessel. Patients that have at least one lesion with a diameter of stenosis of 50% or more on visual estimation, feasible (operators judgement) for treatment with PCI in a non-IRA, will be randomised either to the FFR guided complete revascularisation arm or to the staged revascularisation by proven ischemia or persistence of symptoms of angina arm. After randomisation a FFR measurement will be performed in all stenosed non-IRA lesions. In the FFR-guided arm, patients will receive a PCI when FFR measurements in a non-IRA lesion will result in a value of less or equal to 0.80.

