11. Gastrointestinal or genitourinary bleeding within the prior 3 months,
12. Planned elective surgical procedure necessitating interruption of thienopyridines during the first 6 months post enrolment.
13. Patients who are actively participating in another drug or device investigational study, which have not completed the primary endpoint follow-up period.
14. Pregnancy or planning to become pregnant any time after enrolment into this study.
15. Inability to obtain informed consent.
16. Expected lost to follow-up.

Informed consent

[figure not shown]
Informed consent will be obtained according to Good Clinical Practice guidelines prior to the procedure. Oral approval to participate in the trial in presence of a third independent (not involved in the study) person (cathlab or ambulance personnel) before the procedure followed by signature after the procedure is also accepted to avoid further delay of treatment.

Randomisation

Randomisation will take place immediately after culprit vessel PCI. The randomisation will be delivered via closed envelopes. The envelopes will be stratified per centre and provided to the centres with blocks of 30 envelopes. Patients who fulfil the inclusion criteria but that for any reason will not participate in the trial will be followed in a separate register (only in Sweden centres and Maasstad hospital for 1 year, starting per 1 January 2013). These results will be extrapolated for the enrolment duration of the study).

Randomisation envelopes will be prepared by Gothia Forum.

The trial design figure

Abbreviations: STEMI: ST-elevation myocardial infarction, PCI: Percutaneous coronary intervention, FFR: Fractional flow reserve, Non-IRA: Non infarct related artery.

Trial design description

Patients will be enrolled and randomised in a 1:2 fashion between the FFR-guided revascularisation strategy, versus staged non-IRA revascularisation, as indicated from the actual guidelines, after completion of a successful culprit lesion PCI. All patients who present at least one lesion with a stenosis of approximately 50% or more in a non-IRA with a diameter of ≥ 2.0 mm and fulfil the inclusion and exclusion criteria will be enrolled.

All patients will receive a FFR measurement in all stenosis of approximately 50% or more in a non-IRA with a diameter of ≥ 2.0 mm

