In the FFR-guided complete revascularisation strategy group all flow limiting ($FFR \leq 0.80$) lesions will receive treatment by PCI and stenting. The non-IRA PCI should be performed during the same intervention. Exceptions can be made for complex lesions where the operator estimates that the revascularisation procedure will require significant contrast overload which may lead to deterioration of cardiac and renal function of the patient. Such procedures can be performed in a second procedure which should take place within the same hospitalisation, preferably within 72 hours.

All lesions with a FFR measurement of >0.80 will not be treated.

In the randomised to guidelines group the procedure will stop after the FFR measurements and the patient will be referred to his treating cardiologist who will decide whether a staged PCI of the non-IRA artery should take place. The treating cardiologist will be blinded for the FFR measurements (but not angiographic imaging) and must make a decision based on conventional non-invasive ischemia detecting tests or clinical signs and symptoms i.e. very typical angina symptoms in patients with angiographic significant stenosis. After the PPCI procedure the FFR values will not be reported in the conventional PCI report but will be registered in the study database only. If the treating cardiologist decides to perform the non-IRA PCI revascularisation, than such treatment should take place within six weeks (45) days from the primary PCI in order to count as a scheduled staged PCI procedure. Any other revascularizations of any lesions after these 6 weeks are identified as unscheduled and therefore counted as an event. Per definition the treating cardiologist should be a different person from the operator.

All revascularisations procedures will be defined as clinically indicated or not clinically indicated by the independent clinical event committee. Non clinically indicated revascularisation will be counted as an event.

Blinding for the FFR results is required to perfectly mimic the standard care treatment in the randomised to guidelines group and avoid bias in further decision tree.

Blinding for the FRR results in this group allows for the following subgroup (shown in figure 2) comparisons and will try to give answers to following dilemmas in the treatment of STEMI patients presenting with multivessel disease:

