A total sample size of 858 patients (286 in the FFR-guided group, 572 in the control group) is sufficient to obtain a power of at least 80% with a two-sided false positive error rate (alpha) of 5% for rejecting the null-hypothesis of no difference when the endpoint incidence is 8% in the FFR guided group vs 14.5% in the control group, using the Pearson Chi-square test for two proportions assuming an asymptotic normal distribution with a normal approximation method.

Considering a 3% loss in follow-up a total of 885 (295/590) patients will be randomised in this trial. Categorical variables will be assessed with the use of χ^2 or Fisher's exact tests, whereas continuous variables will be assessed with the Wilcoxon rank-sum test.

The results in both groups for the primary endpoint as well as for the secondary endpoints will be presented as time to event curves (Kaplan-Meyer).

Trial Conduct

Cathlab procedure

The primary PCI will be performed within 12 hr after onset of symptoms, however patients with symptoms for more than 12 hr and ongoing ischemia can also be randomised.

Standard care cathlab techniques and equipment will be used to perform the coronary angiography imaging and primary PCI. Artery puncture site is left at the discretion of the operator, although radial approach is strongly recommended to avoid bleeding complications at the puncture site. A diagram or description of the coronary artery tree will be completed at the end of the procedure to indicate which segments have lesions with approximately 50% or more diameter stenosis. If the lesion extends over more than one segment the most proximal segment should be stated.

Assessment of left ventricle function or wall motion abnormalities are at the discretion of local practice.

Thrombosuction and pre-dilation of the lesion are left at the discretion of operator.

Intracoronary injection of nitrates followed by two orthogonal projections for culprit lesion evaluation and stent size choice are strongly recommended.

Stenting should by protocol be performed. Everolimus Eluting Xience V/ Prime /Expedition should be used in this study as these are at the moment the most safe drug-eluting stents clinically proven in this setting.

Post-dilation will be left at the discretion of the operator.

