After primary PCI, enrolled patients are randomized. FFR measurements will be performed after the randomisation. To guarantee for uniformity of these measurements the RADI (St Jude) FFR system is strongly recommended..

Measurements of ACT before the FFR procedure is recommended.

The protocol for FFR measurement is shown in appendix 1

For the PCI of the non-IRA the same recommendations as for the PCI of the culprit lesion are valid.

Anticoagulant and antithrombotic treatment

Bivaluridin is the anticoagulant of choice in this trial. For dosage see Appendix 2. Previous Heparin administration (eventually during transport in the ambulance) is not a contraindication.

All patients should receive a loading dose of aspirin of 150–300 mg per os or 250 (–500) mg bolus i.v., followed by 75–100 mg daily lifelong.

Prasugrel or Ticagrelor are the P2Y12 inhibitors of choice in treatment of STEMI conform the latest guidelines, therefore we strongly recommend their use in this study. Patients who have received a loading dose of Clopidogrel may receive prior to stenting a loading dose of Prasugrel or Ticagrelor respectively 60 mg and 180mg followed by 10 mg once daily for the prasugrel or 90 mg twice daily for the Ticagrelor in the first 12 months after the last procedure.

The use of IIbIIIa inhibitors is not recommended but can be used as bailout.

Trial Sites

The trial will be performed in big-volume interventional cardiology centres in Europe and Asia.

Other centres in other countries can join in a second timing if needed.

Sites in the Netherlands:

Leading centre:

Maasstad Hospital Rotterdam

Haga Hospital Den Haag

Academisch Medisch Centrum (AMC) Amsterdam

Sites in Sweden:

Gotheborg University Hospital

Sites in Germany:

Herzzentrum Segeberger Kliniken, Bad Segeberg

University Hospital Rostock, Rostock

Herzzentrum Bad Krozingen, Bad Krozingen

Deutsches Herzzentrum, München

Klinikum Ingolstadt, Ingolstadt

Klinikum Links der Weser, Bremen

Sites in Luxembourg:

Centre Hospitalier de Luxembourg

Sites in Norway:

Rigshospitalet University of Oslo

Sites in Singapore:

Tan Tock Seng Hospital

Khoo Teck Puat Hospital

Sites in Poland

Sites in Czech Republic

Trial management

The trial will be performed under supervision of the Steering Committee.

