Appendix 1 FFR protocol

Adenosine during FFR I.C. administration

Drug Group

Anti-arrhythmia

Working

Adenosine is a molecule produced from the human body. It increases the blood flow in the coronary arteries by 200 to 400%. It temporarily blocks the AV node. Further it is a vasodilator. The half-life is a maximum of 30 seconds.

Indications

- FFR-measurement

Contra-indications

- Bronchospasm
- Hypotension
- SSS and AV-block (2-3)

Side Effects

- AV block
- Flushing
- Angina
- Dyspnoe
- Atrial en ventricular arhythmias
- HR increases between 15 and 25%
- Drop in blood pressure up to 6%

Antidote

Theophylline

Dose

Bolus for the RCA: start with 40 mcg, and increase stepwise till max. 100 mcg till no further drop in FFR is obtained.

Bolus for the LCA: start with 60 mcg ,and increase stepwise till max. 100 mcg till no further drop in FFR is obtained.

Step 1

Flacon of Adenosine 500 mg in 100 ml = 5 mg/ml

2 ml (= 10 mg) diluted with NaCl 0,9% to 10 ml

10 mg in 10 ml = 1 mg/ml

Step 2

Take 1 ml diluted with NaCl 0,9% to 10 ml

1 mg in 10 ml = 0,1 mg/ml (= 100 mcg/ml)

Step 3

100 mcg = 1 ml given to the sterile personnel,
who adds to this NaCl 0,9% to 10 ml
100 mcg in 10 ml = 10 mcg/ml

Final Delivery Form

Flacon 100 ml = 500 mg

Extra Attention

- Stop Persantin one day before use
- Inform the patient about possible side effects
- Maximum effect time, 30 to 90 seconds.
- Time for returning to normal ECG 30 to 120 seconds.

Adenosine bij FFR I.V. administration

Drug Group

Anti-arrhythmia

Working

Adenosine is a molecule produced from the human body. It increases the blood flow in the coronary arteries by 200 to 400%. It temporarily blocks the AV node. Further it is a vasodilatator. The half-life is a maximum of 30 seconds.

Indications

- FFR-measurement

Contra-indications

- Bronchospasm
- Hypotension
- SSS and AV-block (2-3)

Side Effects

- AV geleidingsstoornis
- Flushing
- Angina
- Dyspnoe
- Atrial en ventricular arhythmias
- HR increases between 15 and 25%
- Drop in blood pressure up to 6%

Antidote

Theophylline

Dose, see doseing schedule

Mix 400cc NaCl with 500 mg Adenosine
Soloution: 1 mg/cc

Packaging

Flacon 100 ml = 500 mg

Extra Attention

- Administer via a centraal venous sheath.
- Stop Persantin one day before use
- Inform the patient about possible side effects
- Maximum effect time, 30 to 90 seconds.
- Time for returning to normal ECG 30 to 120 seconds.

Dosing Schedule Adenosine during FFR I.V.

Dose 140 mcg/kg/min

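### FFR is measured with the arm known and no lesion list is fixed before allocation: a probably small but avoidable bias in the secondary comparisons by FFR status, not in the primary one

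*Combined protocol and SAP*

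**What the plan says.** The Randomisation section places allocation in the cathlab: "Randomisation will take place immediately after culprit vessel PCI. The randomisation will be delivered via closed envelopes". Two places put FFR after it. The Summary has "After randomisation a FFR measurement will be performed in all stenosed non-IRA lesions", and Trial Conduct (Cathlab procedure) has "FFR measurements will be performed after the randomisation".

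The lesions to be measured are set in the Trial design description: "All patients will receive a FFR measurement in all stenosis of approximately 50% or more in a non-IRA with a diameter of" at least 2.0 mm. The record of such lesions is described under Cathlab procedure: "A diagram or description of the coronary artery tree will be completed at the end of the procedure to indicate which segments have lesions". For controls, the Trial design description adds "In the randomised to guidelines group the procedure will stop after the FFR measurements", and the values go only to the study database.

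The only blinding to FFR described is that of the treating cardiologist, in the control arm, and this person must differ from the operator. For intracoronary adenosine, Appendix 1 tells the operator to "increase stepwise till max. 100 mcg till no further drop in FFR is obtained". The Summary names an angiographic core lab for event adjudication. No reading of FFR tracings blinded to arm is described.

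The Endpoints section defines the primary comparison as a+b versus c to f. Secondary endpoints 2, 3 and 4 are a+c versus d, a versus c, and e versus b+f.

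**The concern.** A subgroup variable compared across arms should be fixed before allocation or obtained without knowledge of it. Here the operator decides which borderline stenoses count as about 50%, and when hyperaemia is sufficient, after learning the arm. The incentives differ. In the FFR arm the value decides treatment during that admission. In controls it changes nothing that day. If effort differed, FFR-positive patients in one arm would not be the same kind of patients as FFR-positive patients in the other.

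At stake are secondary endpoints 2 to 4 and any comparison of randomised arms within FFR status, such as a versus c+d or b versus e+f. The Trial design description gives these subgroup questions as one reason for concealing FFR in controls, and chooses 1:2 allocation to balance the subgroups.

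**Working it through.** **1. Order of events.** The sentence on the lesion diagram stands in the text on angiography and primary PCI, before the sentence on randomisation. So its procedure could be the primary PCI alone. The Trial design description has the control procedure run on to the end of the FFR measurements, which favours the later reading without settling it.
- Later reading: the list is completed after allocation and FFR.
- Earlier reading: the list and the envelope fall at the same moment, the end of culprit PCI, and nothing states which comes first.
- Under both readings FFR is measured with the arm known.

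**2. Which comparisons are exposed.** The primary comparison uses everyone as randomised, so FFR status cannot move a patient between its groups. Endpoints 2 to 4 combine or oppose the arms within FFR status, so they are exposed. The comparison c versus d, also listed in the Trial design description, lies wholly within controls. Arm-dependent measurement cannot make its two groups differ in how FFR was obtained.

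**3. The plan's sample size, as a check on inputs.** With 8% versus 14.5%, 1:2 allocation, two-sided 5% and 80% power, the pooled proportion is (0.08 + 2 × 0.145)/3 = 0.1233. Then

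n(FFR) = [1.960 × √(0.1233 × 0.8767 × 1.5) + 0.842 × √(0.08 × 0.92 + 0.145 × 0.855/2)]² / 0.065² = 286.

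This gives 286 + 572 = 858, and 858/0.97 = 885. Both figures are reproduced.

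**4. Expected groups.** Statistical Considerations gives 50% FFR-positive (stated for controls; applied here to both arms), 70% of FFR-positive controls revascularised, and 50% of FFR-negative controls not revascularised. With 286/572:
- a = b = 286 × 0.5 = 143
- c = 286 × 0.7 = 200.2; d = 286 × 0.3 = 85.8
- e = f = 286 × 0.5 = 143

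**5. Illustration A: FFR-positive controls misread as negative.** The documents give no misclassification rate, so 5% and 10% are assumptions.
- Patients moved: 286 × 0.05 = 14.3; 286 × 0.10 = 28.6.
- Share of e+f: 14.3/300.3 = 4.8%; 28.6/314.6 = 9.1%.
- The treating cardiologist does not see FFR, so the 70% rate should still apply to these patients. The remaining 30% enter f: 4.3 and 8.6.
- The plan adds 20 points of risk only for FFR-positive patients left on medical treatment. Added risk in b+f: 4.3/290.3 × 20 = 0.3 points; 8.6/294.6 × 20 = 0.6 points.

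**6. Illustration B: FFR-negative patients called positive in the FFR arm only.** Assume no treatment effect, FFR-negative risk 8%, FFR-positive risk 12% to 28%, and 5% to 20% misclassified. Observed FFR-positive risk in that arm is (0.5 × p₊ + 0.5 × q × 0.08)/(0.5 + 0.5q).
- q = 0.05, p₊ = 0.12: 11.81%, a shift of −0.2 points.
- q = 0.10, p₊ = 0.28: 26.18%, a shift of −1.8 points.
- q = 0.20, p₊ = 0.28: 24.67%, a shift of −3.3 points, the extreme of the range.

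If FFR-positive patients in that arm were instead called negative, its FFR-negative risk would rise by 0.2 to 3.3 points.

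**7. Would an imbalance be noticed?** With 295 versus 590 randomised and a 50% share in controls, power to detect a different FFR-positive share in the FFR arm is about 10% at 47.5%, 29% at 45% and 81% at 40%. A modest shift would usually pass unseen.

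**The case against.** The strongest defence is that the affected comparisons are not randomised in any case. Groups c and d, and e and f, are separated by the treating cardiologist's later decision. No reordering in the cathlab would make a versus c or e versus b+f unconfounded. This stands and limits what a fix can achieve. It does not justify a second, avoidable bias, and a versus c+d and b versus e+f would be free of the first.

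The protocol also limits discretion. Every qualifying stenosis is to be measured in every patient, the intracoronary titration has a stopping rule, and the intravenous option has a weight-based rate. Sites are trained in pressure measurement, one FFR system is strongly recommended, and a quarter of patients have all variables monitored. These reduce the risk but do not hide the arm from the person measuring.

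Concealing FFR in controls also serves to mimic usual care and to protect later decisions from bias. The operator's knowledge of the arm leaves that purpose intact.

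The current order has a merit too. Because FFR is unknown at allocation, nobody can be left out on its value. Measuring FFR while a site-held envelope is still sealed would give up that protection for the primary comparison.

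**Conclusion.** The point holds in a limited form. FFR status is ascertained with the arm known, no list of qualifying segments is stated to be fixed before allocation, and secondary endpoints 2 to 4 compare groups defined by it. Size and direction cannot be derived from the documents. Carried through at the plan's own rates, an assumed 5% to 10% misreading in controls adds about 0.3 to 0.6 points in b+f. The larger shifts in Illustration B need more extreme assumptions. The bias is probably small, and correcting it is a cheap improvement to secondary analyses.

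A reader might infer three stronger things that the documents do not support:
- That the primary result is biased. It compares whole randomised arms.
- That the lesion record is certainly made after allocation and FFR. The wording allows the end of primary PCI.
- That qualifying lesions can never be verified. Eligibility rests on the baseline angiogram, which precedes randomisation and could be re-read, although no such step is described.

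**What to change.** Amend the two Cathlab procedure statements, and the Summary and Randomisation sections to match:

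1. Before the envelope is opened, the operator records and time-stamps the qualifying non-infarct segments from the baseline angiogram.
2. FFR is required in every listed segment in both arms. A value not obtained is recorded as missing, with the reason.
3. Lesions listed, lesions measured, missing FFR and FFR-positive share are reported by arm. Given the low power shown above, this is description and not proof of balance.

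This removes arm-dependent choice of lesions. It does not conceal the arm during the measurement itself. Measuring FFR before opening the envelope would do so, but is an option only if enrolment is first irrevocably logged with the envelope number, outside the operator's control, and every logged patient is analysed as randomised. Without those safeguards, knowledge of FFR before allocation could bias the primary comparison.

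The cost of steps 1 to 3 is about a minute of documentation before allocation and a short table in the report. No procedure is added, because both arms already receive FFR, and no treatment rule changes.

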- 1) Clinical outcomes differences between PCI treatment vs optimal medical treatment in patients with at least one FFR positive lesion (group c vs group d)
- 2) Staged PCI versus acute (during PPCI) revascularisation of FFR positive lesions (group a vs group c)
- 3) Optimal Medical Treatment versus PCI treatment of FFR negative lesions (group b + f vs group e)

In order to balance the number of patients in these subgroups we chose for a 1:2 randomisation pattern.

[figure not shown]

Figure 2: Subgroups resulting from this randomisation.

Endpoints

Primary endpoint:

Composite endpoint of all cause mortality non-fatal Myocardial Infarction, any Revascularisation and Cerebrovascular Events (MACCE) at 12 months between groups (a+b versus c-f).

Secondary endpoints:

1. Primary endpoint at 24 and 36 months as well as outcomes of each component of the primary endpoint at 12, 24 and 36 months.
2. Primary endpoint rates at 12, 24 and 36 months in the subgroup of patients receiving staged or acute PCI treatment for FFR positive lesions in the non-IRA vs the subgroup of patients with FFR positive lesion that received optimal medical treatment. {figure 2, subgroups (a+c) vs subgroup d}
3. Primary endpoint rates at 12, 24 and 36 months in the subgroup of patients receiving acute PCI treatment for FFR positive lesions in the non-IRA vs the subgroup of patients receiving staged PCI treatment for FFR positive lesions in the non-IRA (figure 2 subgroups a vs c)
4. Primary endpoint rates at 12, 24 and 36 months in the subgroup of patients receiving staged PCI treatment for FFR negative lesions in the non-IRA vs the subgroup of patients not receiving PCI treatment for FFR negative lesions in the non-IRA. (figure 2 subgroups e vs b+ f)
5. Composite endpoint of Cardiac death, Myocardial Infarction, any Revascularisation, Stroke and Major bleeding at 12, 24 and 36 months (NACE i.e. Net Adverse Clinical Events)
6. A composite of hospitalisation for heart failure and unstable angina pectoris at 12, 24, and 36 months
7. All cause mortality or Myocardial infarction at 12, 24 and 36 months

8. Any revascularisation at 12, 24 and 36 months
9. Stent thrombosis at 12 months, 24 and 36 months
10. Bleeding at 48 hr and 12 months.
11. Treatment costs 12 months, 24 and 36 months

Definitions

Death

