Compare Acute is a prospective, multicenter, randomized trial aiming to compare a new strategy in treatment of STEMI in patients with multivessel disease compared to the actual standard of care in respect to the primary endpoint of cardiac death, non fatal myocardial infarction and any revascularization at 12 months.

The event rates for both groups were defined as follows:

In the FFR guided group the event rates were estimated based on data from the COMPARE trial STEMI subgroup analysis where the rates of all death, myocardial infarction, and target lesion revascularisation in the Xience V arm was found to be 6.7 %. Multivessel treatment in the Xience V group occurred at the same frequency as expected in the FFR guided group therefore we estimate a primary endpoint of 7%. Counting a rate of 1% for stroke a primary endpoint rate of 8% is expected.

In the staged, guideline guided group estimations were based on the following assumptions, which represent the combined experience of all participating centres:

- a) 60% of patients will receive a exercise stress test (sensitivity 67%, specificity 70%)³⁴
- b) 20% will receive a nuclear scan (sensitivity 81%, specificity 85-95%)³⁴
- c) 20 % will receive no ischemia detecting test but will be guided by clinical symptoms and angiographic data.

Decision to *revascularisation* will be taken in 70% of patients with positive FFR. Decision to *not perform revascularisation* will be taken in 50% of patients with negative FFR.

Based on the results of the FAME angiographic analysis³⁵ and taking in account that a lesion of > 50% DS will have an equal distribution of FFR negative and positive patients in the staged, guideline guided group.

An event rate of 20 % (mainly due to unplanned revascularisations) on top of standard STEMI treatment event rates is expected for FFR+ non-IRA patients that will receive optical medical treatment only.

Higher event rates are expected also for all patients treated in a staged setting due to periprocedural complications.

Stroke rates of 1.0% are expected in the FFR group and 1.5% (50% more procedures) are expected in the non-FFR guided group.

Based on these assumptions and data, an event rate of 14.5% is expected in the staged, guideline guided non-IRA revascularisation group.

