For ethical and safety reasons, three formal interim analyses will be performed when 25%, 50% and 75% of the suspected number of primary endpoint events in patients allocated to FFR guided revascularisation group or the actual standard of care group have occurred (i.e. after 32, 63 and 95 events, respectively). The independent Data Safety Monitoring Board (DSMB) will review these analyses and inform the Steering Committee. The DSMB will consider the primary endpoint and secondary endpoints consistency, and the consistency of treatment effects across clinically relevant subgroups.

The DSMB will also monitor the study to evaluate if each of the two groups is associated with increased mortality. For these safety analyses, premature termination of the trial should be considered.

The DSMB will consist of 3 members.

First 5 patients in all centres will be fully monitored for all variables.

This will be followed by spot monitoring aiming at a site monitoring for a total of 25% of trial population for 100% of variables and for the rest of the population for 20% of the variables.

Event collection will be done by patients contacts or monitoring of patient charts up to 1 year at 30 and 360 days. Thereafter, event collection will be done by correspondence or telephone contact with all patients at 2 and 3 years. In parallel to this, information from national health registers in respective countries will be used.

Events will be analysed by an independent CRO and will be adjudicated by an independent Clinical Evaluation Committee (CEC).

All sites will undergo training prior to study initiation. Training will cover how to obtain informed consent, randomisation, data entry, the catheter laboratory procedure for guide wire based coronary pressure measurement, and how to complete the electronic case record. Training could be delivered either by a Site Visit or through a single meeting attended by PIs and support staff from all of the sites.

Study duration

The study is expected to finish enrolment in 3.5 years (+/- 2) months from the start date.

We aim to produce the first manuscript (30 day results) at 45 (+/-1) months after the start of the study. The main manuscript is expected at 55 (+/-1) months after the start of the study.

Regulatory approvals

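### The interim looks at 32, 63 and 95 events are not 25%, 50% and 75% of the events the plan's own rates and sample size predict, and no basis for them is given

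*Combined protocol and SAP*

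**What the plan says.** The Trial management section says that "three formal interim analyses will be performed when 25%, 50% and 75% of the suspected number of primary endpoint events" have occurred, counting patients in either randomised group, and then turns the percentages into numbers: "i.e. after 32, 63 and 95 events, respectively". The looks are introduced on ethical and safety grounds, and the DSMB reviews them.

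The inputs for an expected number of events are in Statistical Considerations. For the FFR-guided group: "Counting a rate of 1% for stroke a primary endpoint rate of 8% is expected". For the control group: "an event rate of 14.5% is expected in the staged, guideline guided non-IRA revascularisation group". The numbers of patients are given as "A total sample size of 858 patients (286 in the FFR-guided group, 572 in the control group) is sufficient" and "Considering a 3% loss in follow-up a total of 885 (295/590) patients will be randomised in this trial". The Endpoints section fixes the time point and the comparison: "MACCE) at 12 months between groups (a+b versus c-f".

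The expected total number of events is not stated anywhere, and no derivation of the three counts is shown.

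**The concern.** The sentence gives each look two definitions, a percentage and a count, and presents them as equivalent. They are equivalent only if about 126 primary endpoint events are expected. The planned rates and sample size point to a total well below that, by more than rounding can explain.

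What is at stake is the timing of the formal DSMB reviews. If the true total is lower than the one behind the counts, every look comes later than its label. The third suffers most, because it would leave little of the trial's information still to come. The plan does not say whether the percentage or the count governs when the two disagree.

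**Working it through.** **Inputs.** From Statistical Considerations: rates of 8% (FFR-guided) and 14.5% (control); 286 + 572 = 858 evaluable; 295 + 590 = 885 randomised; two-sided 5%, 80% power, Pearson chi-square. From Trial management: 25/50/75% and 32/63/95. From Endpoints: a 12-month endpoint.

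**Step 1: are the inputs sound?** With 1:2 allocation the mean rate is (0.08 + 2 × 0.145)/3 = 0.1233. The FFR-group size is

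n = [1.960 × √(1.5 × 0.1233 × 0.8767) + 0.8416 × √(0.08 × 0.92 + 0.145 × 0.855/2)]² / 0.065² = (0.7893 + 0.3099)² / 0.004225 ≈ 286.

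The control group is then 572 and the total 858. Allowing for loss, 858/0.97 = 884.5, so 885. The plan's sample size is reproduced exactly.

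**Step 2: which total do the counts imply?** With ordinary rounding:
- 32 at 25% needs a total from 126 to below 130.
- 63 at 50% needs 125 to below 127.
- 95 at 75% needs 126 to below 127.3.

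All three hold only from 126 to just under 127. Rounding up needs more than 125.3 and at most 126. Rounding down is impossible, since 32 would need at least 128 and 63 would need fewer than 128.

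**Step 3: which total do the plan's inputs give?** Events = n(FFR) × 0.08 + n(control) × 0.145.

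| Basis | Expected events | 25% | 50% | 75% |
|---|---|---|---|---|
| 858 evaluable | 22.88 + 82.94 = 105.82 | 26.5 | 52.9 | 79.4 |
| 885 randomised, full follow-up | 23.60 + 85.55 = 109.15 | 27.3 | 54.6 | 81.9 |

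The implied total of 126 is 126/109.15 = 1.15 to 126/105.82 = 1.19 times these. As a pooled rate, 126–127 events are 14.2–14.4% of 885 or 14.7–14.8% of 858, against 12.3% in the plan. With 8% kept in the FFR group, 126 events would need a control rate of (126 − 23.6)/590 = 17.4% or (126 − 22.88)/572 = 18.0%.

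**Step 4: where do the stated counts fall?**

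| Count | Share of 105.82 | Share of 109.15 | Label |
|---|---|---|---|
| 32 | 30.2% | 29.3% | 25% |
| 63 | 59.5% | 57.7% | 50% |
| 95 | 89.8% | 87.0% | 75% |

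After 95 events, 10.8 or 14.2 expected events remain. After a true 75% look, 26.5 or 27.3 remain.

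**Step 5: could another basis give 32/63/95?**
- 14.5% applied to all patients: 858 gives 124.4 (31.1/62.2/93.3; rounded up, 32/63/94). 885 gives 128.3 (32.1/64.2/96.2). Close, but not the stated counts.
- Control group only: 83–86 events. Group sizes swapped: 87–90. Equal allocation: 97–100.
- Endpoint without stroke, as Statistical Considerations words it (7% and 13% after removing the stated stroke rates): 94.4 or 97.4.
- Freedman's event formula with hazard ratio 0.08/0.145 = 0.552 gives 126, but only at 90% power and equal allocation. The plan has 80% and 1:2.

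**Step 6: calendar effect, as an illustration.** Assume even accrual over 42 months (the 3.5 years under Study duration) and the two-rate totals. If events come soon after randomisation, a look at fraction f falls at month 42f: month 31.5 for 75%, but 36.6–37.7 for 95 events. If events spread evenly over 12 months, it falls at month 42f + 6 while enrolment is open: 37.5 for 75%. After month 42 the share still to come at month t is (54 − t)²/(24 × 42), so 95 events fall at about month 42.6–43.9, when enrolment has closed. Either way the third look comes some 5–6 months later.

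**The case against.** The best defence is that the plan never says its expected number of events is the two-rate total. A monitoring total can be set at a common rate, and 14.5% is the only standard-care rate in the document. If the 3% lost to follow-up contribute half their time on average, the effective number is 885 × 0.985 = 871.7. Then 871.7 × 0.145 = 126.4, with quarter points 31.6/63.2/94.8, which round to exactly 32/63/95. On that view the counts are not wrong and only their basis is missing.

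This shows a possible route to the figures, but it is conjecture. The plan states neither the common rate nor the half follow-up, and the route ignores the 8% that the plan itself expects in the FFR group. The same follow-up assumption with both planned rates gives 109.15 × 0.985 = 107.5 events. What stands is that the right replacement counts cannot be known until the sponsor names the basis.

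The Definitions section also says that the trial is powered for two definitions of myocardial infarction, and the expected total might depend on which one is used. Only one pair of rates is given, so this cannot be tested.

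Finally, the consequence is limited. The counts can be used as they are, no boundary in the plan depends on exact information fractions, and mortality is monitored separately. That is fair, and it is why the point is minor.

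**Conclusion.** The concern holds, as a minor arithmetic error. Percentages and counts in the same sentence disagree under the plan's own rates and numbers. The counts are 5, 8 and 13 events above 27/55/82 (885 randomised), or 6, 10 and 16 above 26/53/79 (858 evaluable). The looks would then fall at 29–30%, 58–60% and 87–90% of the expected events.

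These sizes assume that the planned 8% and 14.5% hold, that events count only to 12 months, and that the counts are followed. If a pooled 14.5% was intended, the mismatch at the two planned sample sizes is at most two events per look with rounding to the nearest integer, but the basis is still unstated. Sample size, power and the final test do not change.

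**What to change.** Rewrite the sentence in Trial management so that it states the expected total number of primary endpoint events, the rates and number of patients behind it, the 12-month window and the rounding rule, and says whether the percentage or the count governs. Then set the counts to match, to the nearest integer:

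- Planned rates, 885 randomised with full follow-up: 27/55/82.
- Planned rates, 858 evaluable: 26/53/79.
- If a pooled 14.5% was intended: say so, and use 32/64/96 for 885 or 31/62/93 for 858.
- If 32/63/95 rests on some other calculation: state that calculation and correct the percentages or the counts to agree with it.

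The cost is one corrected sentence, with no extra patients and no change to the power or the final test.
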